### 13. ADVERSE EVENTS

#### 13.1. Definitions and Classifications

**Adverse Event (AE)** – An AE is “any untoward medical occurrence, unintended disease or injury, or untoward clinical signs (including abnormal laboratory findings) in subjects, users or other persons, whether or not related to the investigational medical device.”

**Note:** This definition includes events related to the investigational medical device or the comparator, and to the procedures involved. For users or other persons, this definition is restricted to events related to investigational medical devices.

An AE includes any condition (including a pre-existing condition) that:

1. Was not present prior to the study, but appeared or reappeared following initiation of the study.
2. Was present prior to the study but worsened during the study. This would include any condition resulting from concomitant illnesses, reactions to concomitant medications, or progression of disease states.

**Note:** Pregnancy must be documented as an adverse event and must be reported to the clinical monitor and to the Sponsor immediately upon learning of the event.

**Serious Adverse Event (SAE)** – An SAE is any adverse event that led to any of the following:

- Death
- Serious deterioration in the health of the subject that resulted in any of the following:
  - Life-threatening illness or injury
  - Permanent or persistent impairment of a body structure or a body function
  - Hospitalization or prolongation of patient hospitalization
- Medical or surgical intervention to prevent life-threatening illness or injury or permanent impairment to a body structure or a body function.

# Clinical Study Protocol

## Johnson & Johnson Vision Care, Inc.

- Chronic disease
- Foetal distress, foetal death or a congenital physical or mental impairment of birth defect.

Diagnoses and conditions that are considered Ocular Serious Adverse Events include, but not limited to:

- Microbial Keratitis (MK)
- Iritis (including cells in the anterior chamber)
- Permanent decrease in best spectacle corrected visual acuity equivalent to 2 acuity lines or greater
- Central Corneal Opacity
- Central Corneal Neovascularization
- Uveitis
- Endophthalmitis
- Hypopyon
- Hyphemia
- Penetration of Bowman's Membrane
- Persistent Epithelial Defect
- Limbal cell Damage leading to Conjunctivalization

**Significant Adverse Events** – are defined as events that are symptomatic and warrant discontinuation (temporary or permanent) of the contact lens wear

Diagnoses and conditions that are considered Ocular Significant Adverse Events include, but not limited to the following:

- Contact Lens Induced Peripheral Ulcer (CLPU)
- Significant Infiltrative Events (SIE)
- Superior Epithelial Arcuate Lesions (SEALs)
- Any Temporary Loss of > 2 Lines of BSCVA
- Other grade 3 or higher corneal findings, such as abrasions or edema
- Non-contact lens related corneal events - e.g. Epidemic Keratoconjunctivitis (EKC)
- Asymptomatic Corneal Scar
- Any corneal event which necessitates temporary lens discontinuation > 2 weeks

**Non-Significant Adverse Events** – are defined as those events that are usually asymptomatic and usually do not warrant discontinuation of contact lens wear but may cause a reduction in wear time. However, the Investigator may choose to prescribe treatment as a precautionary measure.

Diagnoses and conditions that are considered Ocular Non-Significant Adverse Events include, but not limited to the following:

- Non-significant Infiltrative Event (NSIE)
- Contact Lens Papillary Conjunctivitis (CLPC)
- Superficial Punctate Keratitis (SPK)

# Clinical Study Protocol

## Johnson & Johnson Vision Care, Inc.

- Conjunctivitis: Bacterial, Viral, Allergic
- Blepharitis
- Meibomianitis
- Contact Dermatitis
- Localized Allergic Reactions
- Any corneal event not explicitly defined as serious or significant adverse event, which necessitates temporary lens discontinuation < 2 weeks

**Adverse Device Effect (ADE)** – An ADE is an “adverse event related to the use of an investigational medical device.”

**NOTE 1: This definition includes adverse events resulting from insufficient or inadequate instructions for use, deployment, implantation, installation, or operation, or any malfunction of the investigational medical device.**

**NOTE 2: This definition includes any event resulting from use error or from intentional misuse of the investigational medical device.**

**Unanticipated Adverse Device Effect (UADE)** – A UADE is any serious adverse effect on health or safety or any life-threatening problem or death caused by, or associated with, the test article, if that effect, problem, or death was not previously identified in nature, severity, or degree of incidence in the investigational plan, Investigator’s Brochure or protocol, or any other unanticipated serious problem associated with the test article that relates to the rights, safety and welfare of subjects.

### 13.2. Assessing Adverse Events

In conjunction with the medical monitor, the Investigator will evaluate adverse events to ensure the events are categorized correctly. Elements of categorization will include:

- Seriousness/Classifications (see definition in section 13.1).
- Causality or Relatedness – i.e. the relationship between the test article, study treatment or study procedures and the adverse event (not related, unlikely related, possibly related, or related - see definition in section 13.2.1).
- Adverse Event Severity – Adverse event severity is used to assess the degree of intensity of the adverse event (mild, moderate, or severe - see definition in section 13.2.2).
- Outcome – not recovered or not resolved, recovering or resolving, recovered or resolved with sequelae, recovered or resolved, death related to adverse event, or unknown.
- Actions Taken – none, temporarily discontinued, permanently discontinued, or other.

#### 13.2.1. Causality Assessment

**Causality Assessment** – A determination of the relationship between an adverse event and the test article. The test article relationship for each adverse event should be determined by the investigator using these explanations:

- Not Related- An adverse event that is not related to the use of the test article, study treatment or study procedures.

# Clinical Study Protocol

## Johnson & Johnson Vision Care, Inc.

- Unlikely Related – An adverse event for which an alternative explanation is more likely, e.g. concomitant treatment, concomitant disease(s), or the relationship of time suggests that a causal relationship is not likely.
- Possibly Related – An adverse event that might be due to the use of the test article, or to the study treatment or study procedures. An alternative explanation, e.g. concomitant treatment, concomitant disease(s), is inconclusive. The relationship in time is reasonable. Therefore, the causal relationship cannot be excluded.
- Related – An adverse event that is listed as a possible adverse effect (device) or adverse reaction (drug) and cannot be reasonably explained by an alternative explanation, e.g. concomitant treatment of concomitant disease(s). The relationship in time is very suggestive, e.g. it is confirmed by de-challenge and re-challenge.

### 13.2.2. Severity Assessment

**Severity Assessment** – A qualitative assessment of the degree of intensity of an adverse event as determined by the Investigator or reported to him/her by the subject. The assessment of severity is made irrespective of test article, study treatment or study procedure relationship or seriousness of the event and should be evaluated according to the following scale:

- Mild – Event is noticeable to the subject but is easily tolerated and does not interfere with the subject's daily activities.
- Moderate – Event is bothersome, possibly requiring additional therapy, and may interfere with the subject's daily activities.
- Severe – Event is intolerable, necessitates additional therapy or alteration of therapy and interferes with the subject's daily activities.

### 13.3. Documentation and Follow-Up of Adverse Events

The recording and documenting of adverse events (ocular and non-ocular) begin when the subjects are exposed to the test article, study treatment or study procedure. Adverse events reported before the use of test article, start of study treatment, or study procedures will be recorded as medical history. However, if the condition deteriorates at any time during the study it will be recorded and reported as an AE. Untoward medical events reported after the subject's exit from the study will be recorded as adverse events at the discretion of the Investigator.

Upon finding an adverse event, the Principal Investigator will document the condition in the subject record and in the eCRFs and complete the Adverse Event eCRF.

Complete descriptions of all adverse events must be available in the subject record. All Adverse Events including local and systemic reactions not meeting the criteria for "serious adverse events" shall be captured on the appropriate case report form or electronic data system. All adverse events occurring while the subject is enrolled in the study must be documented appropriately regardless of relationship.

It is the Investigator's responsibility to maintain documentation of each reported adverse event. All adverse events will be followed in accordance with applicable licensing requirements. Such documentation will include the following:

- Adverse event (diagnosis not symptom).

# Clinical Study Protocol

## Johnson & Johnson Vision Care, Inc.

- Drawings or photographs (where appropriate) that detail the finding (e.g., size, location, and depth, etc.).
- Date the clinical site was notified.
- Date and time of onset.
- Date and time of resolution.
- Adverse event classification, severity, and relationship to test articles, as applicable.
- Treatment regimen instituted (where appropriate), including concomitant medications prescribed, in accordance with applicable licensing requirements.
- Any referral to another health care provider if needed.
- Outcome, ocular damage (if any).
- Likely etiology.
- Best corrected visual acuity at the discovery of the event and upon conclusion of the event, if the AE is related to the visual system.

Upon discovery of an AE that is deemed ‘possibly related’ or ‘related’ to the test article or study procedures (whether related to the visual system or not), an AE review form [REDACTED] must be completed. Additional dated and initialed entries should be made at follow-up evaluations. Separate forms must be completed for each eye if the AE is bilateral.

In addition, if an infiltrate(s) is present, he/she will complete the Corneal Infiltrate Assessment eCRF. Where necessary, a culture of the corneal lesion will be collected to determine if the infection is microbial in nature. If cultures are collected, the date of culture collection and laboratory utilized will be recorded.

Changes in the severity of an AE shall be documented to allow an assessment of the duration of the event at each level of intensity to be performed. Adverse events characterized as intermittent require documentation of the onset and duration of each episode. Changes in the assessment of relationship to the Test Article shall also be clearly documented.

Subjects who present with an adverse event shall be followed by the Investigator, within licensure, until all signs and symptoms have returned to pre-treatment status, stabilized, or been satisfactorily resolved. If further treatment beyond licensure is required, the patient will be referred to the appropriate health care provider. The Investigator will use his/her clinical judgment as to whether a subject reporting with an adverse event will continue in the study. If a subject is discontinued from the study, it will be the responsibility of the Investigator to record the reason for discontinuation. The Investigator will also document the adverse event appropriately and complete the Adverse Event eCRF. Any subjects with ongoing adverse events related to the test article, study treatment or study procedures, as of the final study visit date, should be followed to resolution of the adverse event or until referral to an appropriate health care provider, as recommended by the Investigator. Non-ocular adverse events that are not related to the test article, study treatment, or study procedures may be recorded as “ongoing” without further follow-up.

# Clinical Study Protocol

## Johnson & Johnson Vision Care, Inc.

### 13.4. Reporting Adverse Events

The Investigator will notify the Sponsor of an adverse event by e-mail, facsimile, or telephone as soon as possible and no later than 24 hours from discovery for any serious /significant adverse events, and 2 days from discovery for any non-significant adverse event. In addition, a written report will be submitted by the Principal Investigator to the IEC/IRB according to their requirements (section 13.4.2). The report will comment whether the adverse event was considered to be related to the test article, study treatment or study procedures.

#### 13.4.1. Reporting Adverse Events to Sponsor

##### Serious/Significant Adverse Events

The Investigator will inform the sponsor of all serious/significant adverse events occurring during the study period as soon as possible by e-mail or telephone, but no later than 24 hours following discovery of the event. The Investigator is obligated to pursue and obtain information requested by the Sponsor in addition to that information reported on the eCRF. All subjects experiencing a serious/significant adverse event must be followed up and all outcomes must be reported.

When medically necessary, the Investigator may break the randomization code to determine the identity of the treatment that the subject received. The Sponsor and study monitor should be notified prior to unmasking the test articles.

In the event of a serious/significant adverse event, the Investigator must:

- Notify the Sponsor immediately.
- Obtain and maintain in the subject's records all pertinent medical information and medical judgment for colleagues who assisted in the treatment and follow-up of the subject.
- Provide the Sponsor with a complete case history which includes a statement as to whether the event was or was not related to the use of the test article.
- Notify the IEC/IRB as required by the IEC/IRB reporting procedure according to national regulations.

##### Unanticipated (Serious) Adverse Device Effect (UADE)

In the event of an Unanticipated (Serious) Adverse Device Effect (UADE), the Investigator will submit a report of the UADE to the Sponsor and IEC/IRB as soon as possible, but no later than 24 hours after the Investigator first learns of the effect. This report is in addition to the immediate notification mentioned above.

The Sponsor must conduct an evaluation of the UADE and must report the results of the evaluation to FDA, the IEC/IRB and participating Investigators within 10 working days after the Sponsor first receives notification of the effect.

##### Non-Serious Adverse Events

All non-serious adverse events, including non-serious adverse device effects, will be reported to the sponsor by the Investigator no later than 2 days from discovery.

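### Significant but non-serious adverse events carry two sponsor-reporting deadlines, 24 hours and 2 days, and the passages need to be reconciled

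*Combined protocol and SAP*

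**What the plan says.** Section 13.1 (Definitions and Classifications) sets out three ocular classes. The significant class is separate from the serious one and has its own list, which includes contact lens induced peripheral ulcer, significant infiltrative events, superior epithelial arcuate lesions, and other corneal findings of grade 3 or above.

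The deadlines for telling the sponsor appear in three places:

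- Section 13.4 gives both limits in one sentence: "no later than 24 hours from discovery for any serious /significant adverse events, and 2 days from discovery for any non-significant adverse event".
- Section 13.4.1, in its paragraph on the serious and significant classes, says: "The Investigator will inform the sponsor of all serious/significant adverse events occurring during the study period". The outer limit it sets is "but no later than 24 hours following discovery of the event".
- Section 13.4.1, in its closing paragraph on the non-serious class, says: "All non-serious adverse events, including non-serious adverse device effects, will be reported to the sponsor by the Investigator no later than 2 days". This limit, too, is counted from the time of discovery.

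Section 13.1 also uses the length of lens discontinuation to sort some corneal events. The significant list has "Any corneal event which necessitates temporary lens discontinuation > 2 weeks". The non-significant list takes corneal events not defined elsewhere as serious or significant "which necessitates temporary lens discontinuation < 2 weeks".

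**The concern.** The first two places divide events by significance and the third divides them by seriousness. The two divisions do not coincide, because the significant class sits between serious and non-significant. Events in that middle class are named in the 24-hour rule and swept into the 2-day rule.

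These are the ocular events a sponsor would want to hear of promptly. Section 16.4 provides for no data monitoring committee, and Section 11 has the sponsor evaluate all adverse events and terminate the investigation, or the affected part, if an event presents an unreasonable risk. That oversight depends on site reports, and dispensing runs over only 2 to 3 months. The separate Medical Monitor section does not settle the matter: its 24-hour notice covers serious adverse events only.

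**Working it through.** The documents give no sample-size, power or error-rate figure on this point to reproduce. The check sets the deadlines side by side by class.

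| Event class (13.1) | 13.4 | 13.4.1, Serious/Significant | 13.4.1, Non-Serious |
|---|---|---|---|
| Serious | 24 h | 24 h | not covered |
| Significant, not serious | 24 h | 24 h | 2 days |
| Non-significant | 2 days | not covered | 2 days |

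The first and third rows agree across the sections. Only the middle row conflicts.

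Size of the conflict: 2 days × 24 = 48 hours, and 48 − 24 = 24 hours. For a significant, non-serious event reported *t* hours after discovery:

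- *t* ≤ 24: all three passages are met.
- 24 < *t* ≤ 48: the Non-Serious paragraph is met; 13.4 and the Serious/Significant paragraph are breached.
- *t* > 48: all three are breached.

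An event on the significant list that also meets the serious definition is outside the conflict, since the Non-Serious paragraph no longer reaches it.

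Duration entries, with *d* the days of lens discontinuation for a corneal event not otherwise listed:

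- *d* > 14: significant.
- *d* < 14: non-significant.
- *d* = 14: neither entry applies.

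The class decides which 13.4 deadline applies, so the unassigned value also has no clear deadline from these two entries.

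**The case against.** The best defence of the text is that the conflict is narrow. The 24-hour rule for significant events is stated twice, and the Serious/Significant paragraph adds immediate notification. A site reporting within 24 hours satisfies everything, and a careful reader would prefer the rule that names the class to a general sentence. This limits the size of the problem but does not remove it: the Non-Serious paragraph has its own heading, contains no exception, and gives a site written permission to take 2 days. On the duration entries, the general definition of a significant event (symptomatic and warranting discontinuation) and the non-exhaustive lists may let an investigator place a 2-week case. The two entries themselves do not.

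A reader might infer more than the documents support.

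- *That no subject can reach the 2-week boundary.* Table 3 puts Visit 3 at (3−1)+(7−1) = 8 to (3+1)+(7+1) = 12 days after Visit 1. But Section 4.1 gives 12±2 days, which is 10 to 14 days if counted from Visit 1, and Table 5 treats a visit up to 2 days out of window as a minor deviation (12+2 = 14 days, or 16 if both visits run late). More importantly, the criterion is the discontinuation an event necessitates, which an investigator can judge in advance and, under Section 13.2, categorises with the medical monitor. Nor is follow-up capped at Visit 3: Sections 7.3 and 13.3 continue it to resolution or stabilisation. A short discontinuation can also be classed well before Visit 3.
- *That events referred at exit drift into the milder class.* Section 13.3 says a related event ongoing at the final visit "should be followed to resolution of the adverse event or until referral to an appropriate health care provider", which sits awkwardly beside 13.4.1: "All subjects experiencing a serious/significant adverse event must be followed up and all outcomes must be reported". But 13.3 also requires the resolution date, the outcome and, for events of the visual system, best-corrected acuity at the event's conclusion. A safety profile biased towards the milder class, or misclassified acuity loss, is not shown. Permanent and temporary acuity loss are in any case both on the 24-hour clock in 13.4.
- *That the co-primary safety result is affected.* Sections 2.2, 2.3 and 14.5 count slit-lamp grade, not adverse event class or reporting time. Grade 3 or higher corneal findings are listed as significant in their own right and do not depend on the 2-week rule.

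**Conclusion.** The deadline conflict stands. Significant but non-serious events have a 24-hour limit in two places and a 2-day limit in a third, a difference of up to 24 hours for each such event. The conclusion rests on reading the Non-Serious paragraph as written, that is, as covering every event that does not meet the serious definition. The practical risk is later notice of an ocular safety signal from a site that was following the protocol; how often this would happen cannot be derived from the documents.

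The unassigned case of exactly 2 weeks is a minor drafting gap. Neither defect changes an endpoint, an estimate, the power or the error rate. Both should be corrected because the text is operative safety wording and the correction is small.

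**What to change.** Reconcile the last paragraph of 13.4.1 with 13.4 and the Serious/Significant paragraph, so that each class has one deadline. One way is to limit the heading and sentence of the 2-day paragraph to events that are neither serious nor significant, using the term non-significant as 13.4 already does, and to adjust its reference to device effects to match.

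In 13.1, reconcile the two duration entries so that every length of lens discontinuation falls in exactly one class. Which side takes exactly 2 weeks is for the sponsor's clinical team to decide.

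The cost is a few words in a protocol revision, its submission to the ethics committee or review board, and a short notice to sites. No visits, assessments or analyses change, and no new reporting rule is needed.

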# **Clinical Study Protocol**

## **Johnson & Johnson Vision Care, Inc.**

### **13.4.2. Reporting Adverse Events to the Responsible IEC/IRB and Health Authorities**

Adverse events that meet the IEC/IRB requirements for reporting must be reported within the IEC/IRB's written guidelines. Each clinical site will refer to and follow any guidelines set forth by their Approving IEC/IRB. Each clinical site will refer to and follow any guidelines set forth by their local governing Health Authorities.

The Sponsor will report applicable Adverse Events to the local health authorities according to the written guidelines, including reporting timelines.

### **13.5. Event of Special Interest**

None

### **13.6. Reporting of Pregnancy**

Subjects reporting pregnancy (by self-report) during the study will be discontinued after the event is recorded as an Adverse Event. Once discontinued, pregnant participants and their fetuses will not be monitored for study related purposes. Pregnant participants are not discontinued from contact lens or solution related studies for safety concerns, but due to general concerns relating to pregnancy and contact lens use. Specifically, pregnant women are discontinued due to fluctuations in refractive error and/or visual acuity that occur secondary to systemic hormonal changes, and not due to unforeseen health risks to the mother or fetus.

